
## Objectives

List your research objectives. Please include a summary of intended research objectives in the box below.

Aim 1: Determine the rate and degree muscle wasting in critically ill patients with AKI-RRT vs historic ICU controls without AKI during ICU stay. Hypothesis 1: Patients with AKI-RRT have faster decline in rectus femoris and tibialis anterior muscle size compared to controls .

Aim 2: Determine the trajectory of muscle recovery in patients following an episode of AKI-RRT compared to matched controls by measuring muscle mass, muscle strength and power, and functional status in patients at discharge and at 1 and 3 months thereafter. Hypothesis 2: Patients with AKI-RRT will have a slower trajectory of muscle recovery following ICU discharge compared to matched patients without AKI.

Aim 3: Use trend analysis to determine that changes in plasma amino acid levels on RRT correlate with lean muscle loss during AKI-RRT and predict lack of muscle recovery at 1 and 3 months. Hypothesis 3: Trends in amino acid levels during treatment with RRT will correlate with MKUS determinations of lean body mass in the short-term and will predict lack of muscle recovery at 1 and 3 months.

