**RISK LEVEL****0 unresolved comment(s)**

Indicate which of the categories listed below accurately describes this protocol

- (Risk Level 1) Not greater than minimal risk
- (Risk Level 2) Greater than minimal risk, but presenting the prospect of direct benefit to individual subjects
- (Risk Level 3) Greater than minimal risk, no prospect of direct benefit to individual subjects, but likely to yield generalizable knowledge about the subject's disorder or condition.
- (Risk Level 4) Research not otherwise approvable which presents an opportunity to understand, prevent, or alleviate a serious problem affecting the health or welfare of subjects.

\*"Minimal risk" means that the probability and magnitude of harm or discomfort anticipated in the research are not greater in and of themselves from those ordinarily encountered in daily life or during the performance of routine physical or psychological examination or tests.

Refer to [UK's guidance document](#) on assessing the research risk for additional information.

**SUBJECT DEMOGRAPHICS****0 unresolved comment(s)**Age level of human subjects: (i.e., 6 mths.; 2yrs., etc.)  to **Study Population:**

Describe the characteristics of the subject population, including age range, gender, ethnic background and health status. Identify the criteria for inclusion and exclusion.

Provide the following information:

- A description of the subject selection criteria and rationale for selection in terms of the scientific objectives and proposed study design;
- A compelling rationale for proposed exclusion of any sex/gender or racial/ethnic group;
- Justification for the inclusion of vulnerable groups such as children, prisoners, adults with impaired consent capacity, or others who may be vulnerable to coercion or undue influence.

Please consider these resources:

[NIH Diversity Policy](#)

[FDA Diversity Guidance](#) 

Population will include adult ICU patients.

Inclusion criteria are as follows: AKI requiring RRT, with RRT being initiated within 48 hours of ICU admission.

Exclusion criteria are as follows: RRT of any type prior to ICU admission, underlying muscle disorders/atrophy, including quadriplegia or hemiplegia, history of stroke with residual muscle deficits, liver cirrhosis, alcohol dependence, active malignancy within 1 year, burns, or other baseline neuromuscular disease, pregnant patients, or anticipated inability to engage in weight-bearing testing after discharge (e.g., traumatic/orthopedic surgery).

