Acute skeletal muscle wasting is a common consequence of critical illness that occurs in up to 65% of patients admitted to the ICU. Critical illness myopathy (CIM), defined as a deficit in muscle size and strength that develops as a result of an ICU admission, is associated with high rates of short- and long-term morbidity and mortality, including decreased quality of life (QoL) due to persistent functional mobility impairments and inability to perform simple activities of daily living. Muscle dysfunction in the critically ill population is driven by underlying changes in cellular and molecular mechanisms leading to a net catabolic state. Rapid reductions in skeletal mass and strength lead to an increased risk of poor patient outcomes, including physical disability and mortality. The diagnosis of CIM in patients with acute respiratory failure or traumatic injury significantly increases the risk of in-hospital and long-term mortality. Recent data suggests that patients lose, on average, 19-27% of rectus femoris muscle size in the first ten days of critical illness. Little is known, however, about the significance of these changes in a subset of critically ill patients with acute kidney injury (AKI) requiring renal replacement therapy (RRT), also known as dialysis. The gold standard for assessing CIM is measurement by muscle biopsy or the analysis of psoas muscle area on a single cross-sectional CT imaging at the level of the L3 vertebra. Musculoskeletal ultrasound (MKUS), a non-invasive alternative, has gained significant traction over the last decade for assessing muscle in patients with critical illness. Studies have demonstrated that MKUS has excellent inter-rater reliability and high clinical utility, and have suggested that MKUS has strong construct validity. Recent data suggests that MKUS can be reliably performed at the ICU bedside, and our preliminary data suggests that graduate students in a healthcare-related field can reliably be trained to assess muscle mass in the ICU using MKUS in as little as 8 hours of training. Changes in rectus femoris size and quality (echo intensity) measured by MKUS were strongly correlated to muscle biopsies in patients with critical illness. In addition, MKUS measures have been shown to have clinical relevance. In a study of 102 surgical ICU patients, muscle wasting determined by MKUS was associated with increased rates of mortality and skilled nursing facility discharge. Acute kidney injury (AKI) is a commonly encountered condition that complicates 22.7% of all inpatient hospital admissions. More than half of all ICU admissions develop AKI, and 13.5% of all ICU patients will require renal replacement therapy (AKI-RRT) during their ICU stay. AKI is associated with poor short- and long-term prognosis. Even Stage 1 AKI is associated with a 10-fold increase in hospital mortality, and AKI-RRT has an in-hospital mortality rate >50%, making AKI-RRT one of the deadliest patient conditions encountered in U.S. hospitals. Even after discharge, patients with AKI continue to have worse outcomes. A meta-analysis of two million patients evaluating outcomes at least a year after admission showed that in-hospital AKI increased the risk of death. Despite how commonly AKI is observed and despite poor long-term outcomes, the rate of outpatient follow-up in this cohort is low. Therefore, patients with AKI are a high-risk, but underserved, group of patients that warrant further study and intervention. AKI of any stage is known to alter tissue utilization of amino acids. Studies have demonstrated that amino acid levels are reduced in AKI, and multiple, non-essential amino acids become conditionally essential. In addition, AKI leads to a state of increased amino acid oxidation, but reduced amino acid transport into muscle. Use of RRT may further exacerbate the issue by removing significant quantities of amino acids from the plasma. Amino acids are small and easily filtered during RRT, so daily losses of amino acids in effluent can be immense at up to 18 grams daily. While cross-sectional analyses demonstrate high clearance levels of amino acids during RRT, there are currently no published longitudinal data regarding amino acid levels. Because skeletal muscle is the major deposit of protein molecules, with nearly 60% of total body protein in humans, we hypothesize that patients with AKI-RRT are at even higher risk of CIM than critically ill controls without AKI.

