This is a prospective, non-blinded, non-randomized study to assess the impact of CRRT on critical illness muscle wasting. As the study is observational and non-interventional in nature, there will be no placebo administered in the course of the study. Patients will be identified based on conversations with ICU and Nephrology consult teams (in addition to chart screening) to determine which patients are likely to receive RRT therapy due to AKI and critical illness. In the first aim, patients will undergo musculoskeletal ultrasound (MKUS) assessments within 24 hours of CRRT initiation, and again at 48 hours and 168 hours. In addition, blood will be drawn at these timepoints and stored for later analysis. In Aim 2, the trajectory of muscle mass recovery will be determined through visits at the time of hospital discharge (to be completed within the hospital), and then at 1 and 3 months thereafter, which will entail separate visits. At these sessions, patients with AKI-RRT and matched controls will undergo measurements of muscle mass, strength, and function at hospital discharge and at 1- and 3-months following discharge. Measurements will include MKUS to determine CSA and muscle echogenicity in the RF and TA muscles. We will evaluate muscle strength by measuring: 1) Medical Research Council sum score (MRC-ss), a measure of global peripheral muscle strength that is the current clinical standard for diagnosing ICU-AW34, 2) Maximal isometric knee extensor and dorsiflexion muscle strength measured as peak force production and rate of force development38, and 3) Maximal isometric grip strength 40. Muscle power will be measured by the repetitive 5x sit-to stand test a reliable and validate measure of lower-extremity power. Physical function and frailty will be measured using 1) the Short Performance Physical Battery (SPPB), 2) six-minute walk test (6MWT), and 3) Clinical Frailty Scale. SPPB is a performance-based composite test with a total of 12 points including components of balance, chair to stand test, and 4-meter habitual gait speed. The 6-MWT assesses the distance a subject can walk in six minutes providing a global marker of physical function and representation of cardiopulmonary endurance. We will summarize descriptive statistics at each timepoint including mean and standard deviation or median and interquartile range, as appropriate. Independent t-tests and Mann-Whitney U tests for non-parametric data will be used as appropriate to compare differences in the testing outcomes between cases and controls at each timepoint. Two-way repeated measures ANOVA will be performed to assess the within change in muscle metrics over time and between group comparisons to understand the trajectories of muscle recovery.

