## Research Procedures

Describe how the research will be conducted.

- What experience will study participants have?
- What will study participants be expected to do?
- How long will the study last?
- Outline the schedule and timing of study procedures.
- Provide visit-by-visit listing of all procedures that will take place.
- Identify all procedures that will be carried out with each group of participants.
- Describe deception and debrief procedures if deception is involved.

Differentiate between procedures that involve standard/routine clinical care and those that will be performed specifically for this research project. List medications that are explicitly forbidden or permitted during study participation.

What RRT subjects will be asked to do/what happens in the study (in sequential order):

- Blood and effluent will be collected at the start of CRRT, at 48 hours, and on day 7 or ICU discharge, whichever comes first. The blood draw for research is 5 mL per draw.
- At hospital discharge, the patient will undergo a series of muscle strength and function tests including 1)Medical Research Council sum score (MRC-ss), a measure of global peripheral muscle strength that is the current clinical standard for diagnosing ICU-AW, 2) Maximal isometric knee extensor and dorsiflexion muscle strength measured as peak force production and rate of force development, and 3) Maximal isometric grip strength. Muscle power will be measured by the repetitive 5x sit-to stand test a reliable and validate measure of lower-extremity power. Physical function and frailty will be measured using 1) the Short Performance Physical Battery (SPPB), 2) six-minute walk test (6MWT), and 3) Clinical Frailty Scale. SPPB is a performance-based composite test with a total of 12 points including components of balance, chair to stand test, and 4-meter habitual gait speed.

The time period over which procedures will occur:

- Ultrasound will be completed at 2 time points: baseline (CRRT initiation) and 7 days after CRRT initiation OR ICU discharge (whichever comes first)
- Muscle strength/function will be assessed at hospital discharge, and at 1 and 3 months thereafter.

The time commitment for the subject for individual visits/procedures

- The time commitment will be 10-20 minutes for 2 ultrasound procedures as above, and the time needed to collect the research blood and effluent, which is likely to be <10 minutes daily for 7 days or until ICU discharge, whichever is first.

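### Aim 1 times case scans from CRRT start, which the historic controls do not have, so the two groups' muscle loss can be measured over different phases of critical illness

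*Protocol*

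**What the plan says.** The Objectives section states Aim 1 as "Determine the rate and degree muscle wasting in critically ill patients with AKI-RRT vs historic ICU controls without AKI during ICU stay". Hypothesis 1 is that cases decline faster in rectus femoris and tibialis anterior size.

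The Study Population criteria define the cases by "AKI requiring RRT, with RRT being initiated within 48 hours of ICU admission" and exclude "RRT of any type prior to ICU admission".

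Case scan times appear twice, and both statements count from CRRT:
- Study Design: "patients will undergo musculoskeletal ultrasound (MKUS) assessments within 24 hours of CRRT initiation, and again at 48 hours and 168 hours".
- Research Procedures, which lists two scans: "baseline (CRRT initiation) and 7 days after CRRT initiation OR ICU discharge (whichever comes first".

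For the historic controls the protocol gives no index time, scan schedule or alignment rule. The control subjects described under Research Procedures are scanned at hospital discharge and at 1 and 3 months. That schedule serves Aim 2 and supplies no scan during the ICU stay.

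The Background gives the expected course of loss: "patients lose, on average, 19-27% of rectus femoris muscle size in the first ten days of critical illness".

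**The concern.** A rate of loss can be compared between groups only if both are observed over the same stretch of illness, or if the loss has the same proportional speed throughout. Cases are observed from a point that varies by up to three days after ICU admission. Controls without AKI cannot be placed on a CRRT clock, so their scans must be timed from some other origin, most naturally ICU admission. Nothing in the protocol requires the two observation windows to cover the same ICU days.

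If they do not, two groups with identical wasting can show different rates. Depending on the shape of the loss curve, the mismatch could hide the faster decline that Hypothesis 1 looks for or create one. The degree of loss is affected as well, because whatever a case loses between ICU admission and the first scan is never observed.

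**Working it through.** The protocol states no figure for this point, so there is nothing to reproduce. The check is window arithmetic followed by an illustration. It assumes that CRRT is the first form of RRT used.

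**Inputs.** RRT start is 0-48 h after ICU admission (Study Population). The first scan is up to 24 h after CRRT start (Study Design) or at CRRT start (Research Procedures). The last scan is 7 days after CRRT start or at ICU discharge if earlier (Research Procedures). Loss is 19-27% over ten days (Background).

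**Step 1: first case scan, hours since ICU admission.**
- Study Design: earliest 0, latest 48 + 24 = 72 h.
- Research Procedures read literally: earliest 0, latest 48 + 0 = 48 h.

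**Step 2: last case scan.** From 0 + 168 = 168 h (day 7) to 48 + 168 = 216 h (day 9), or earlier at ICU discharge.

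**Step 3: loss before the first scan, if linear.** The daily loss is 19/10 = 1.9 to 27/10 = 2.7 points.
- First scan at 72 h: 3 × 1.9 = 5.7 to 3 × 2.7 = 8.1 points.
- First scan at 48 h: 2 × 1.9 = 3.8 to 2 × 2.7 = 5.4 points.

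**Step 4: illustration with the same true curve in both groups.** Total loss is the midpoint, (19 + 27)/2 = 23% over ten days. Controls are assumed scanned on days 0-7. Cases take the worst case, days 3-9. Observed loss = (loss at last scan − loss at first scan)/(100 − loss at first scan), and the rate is that divided by the days between scans.

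*Front-loaded: half the loss in days 0-3 (assumed), the rest spread evenly.* The first 3 days take 11.5 points, then 11.5/7 = 1.643 points per day.
- Controls: 11.5 + 4 × 1.643 = 18.1%; 18.1/7 = 2.58% per day.
- Cases: 6 × 1.643 = 9.86; 9.86/88.5 = 11.1%; 11.1/6 = 1.86% per day.
- Ratio 1.86/2.58 = 0.72, so cases appear 28% slower.

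*Linear: 2.3 points per day.*
- Controls: 7 × 2.3 = 16.1%; 2.30% per day.
- Cases: 6 × 2.3 = 13.8; 13.8/(100 − 6.9) = 14.8%; 14.8/6 = 2.47% per day.
- Ratio 2.47/2.30 = 1.07, so cases appear 7% faster.

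Under linear loss the total points the other way: 14.8/16.1 = 0.92, about 8% less loss in cases, because six days are compared with seven.

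**Step 5: the same with a 48 h offset (cases on days 2-9).**
- Front-loaded, with the early loss even at 11.5/3 = 3.83 points per day: 7.67 points lost by day 2 and 21.36 by day 9; 13.69/92.33 = 14.8%, or 2.12% per day. Ratio 2.12/2.58 = 0.82.
- Linear: 16.1/95.4 = 16.9%, or 2.41% per day. Ratio 2.41/2.30 = 1.05.

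**Step 6: a different curve shape.** A smooth decelerating curve, loss(t) = L × (1 − e^(−kt))/(1 − e^(−10k)), with L the ten-day loss and k from 0.1 to 0.3 per day (assumed), gives these rates in % per day:

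| Ten-day loss | Curve | Controls, days 0-7 | Cases, days 3-9 | Ratio |
|---|---|---|---|---|
| 19% | linear | 1.90 | 2.01 | 1.06 |
| 19% | k = 0.1 | 2.16 | 1.82 | 0.84 |
| 19% | k = 0.3 | 2.51 | 1.28 | 0.51 |
| 27% | linear | 2.70 | 2.94 | 1.09 |
| 27% | k = 0.1 | 3.07 | 2.68 | 0.87 |
| 27% | k = 0.3 | 3.56 | 1.93 | 0.54 |

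Identical wasting therefore looks about 13% to 49% slower in cases on these decelerating curves, and about 6% to 9% faster if linear.

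**The case against.** The strongest reply is that the document is an IRB application with summary boxes, that a separate detailed protocol is listed among its attachments and is not shown, and that the historic controls' scan days may already match those of the cases. This stands as far as it goes: no bias has been shown, and neither its size nor its sign can be read from the text. It does not remove the point. The historic scans already exist, and no later analysis plan can supply scans on ICU days that were not imaged. The time origin has to be settled when the comparator is chosen.

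A second reply is that CRRT start is the natural origin for a study of the effect of CRRT, and that the 48-hour entry limit already bounds the offset. Both are fair. CRRT start is a defensible exposure origin for cases, but it gives the controls no matching one. The bound leaves an offset of two to three days in a window of about seven.

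Third, the illustration is a worst case: RRT at 48 hours, the first scan a full 24 hours later, and every control scanned at admission. That is correct, and the front-loaded shape has no source in the protocol.

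Three stronger readings are tempting but unsupported:
- A reader might infer that the t-test, Mann-Whitney test and repeated-measures ANOVA under Study Design are the Aim 1 analysis and cannot align ICU days. Those sentences follow the Aim 2 visits, and the ANOVA is tied to recovery, so they cannot be firmly assigned to Aim 1.
- A reader might count 168 hours from a day-3 first scan and put the last scan on day 10. Research Procedures counts seven days from CRRT initiation, so the latest is day 9.
- A reader might conclude that the groups will show different rates. The protocol supports only that they can.

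**Conclusion.** The point holds as a design weakness. As written, Aim 1 contrasts cases on a CRRT clock with controls who have no such clock, and it sets no common origin. The first case scan falls 0-72 hours after ICU admission under Study Design, or 0-48 hours under Research Procedures. The last falls between day 7 and day 9, or earlier at ICU discharge. If loss is linear at the Background's rate, up to 5.7-8.1 points (3.8-5.4 with a 48-hour limit) precede the first case scan.

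In the worst-case illustration, the offset alone moves the apparent rate in cases from about 28% lower to about 7% higher, depending on the curve. These two figures rest on the assumed 23% loss, the assumed curve shapes and controls assumed scanned from day 0. They show that the effect can be material and can go either way. They do not estimate the bias in this study, because the control scan times are not given.

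**What to change.** 1. Record hours from ICU admission to every Aim 1 scan, in cases and in historic controls.
2. Choose the historic controls, and the scans used from them, so that the first scan and the interval cover the same ICU days as the cases.
3. Make the Aim 1 contrast a group-by-time term in a model of muscle size on time since ICU admission, using actual scan times.
4. Reconcile the Study Design and Research Procedures statements of case scan timing, which differ on the baseline window, the number of scans and the ICU-discharge limit.

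The cost is protocol wording and the retrieval of admission and scan times. That these times can be recovered for the historic controls is an assumption, since their dataset is not described. Historic controls without scans on comparable ICU days would drop out, which costs some precision. No clinical procedure changes.

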## Study Design

Describe and explain the study design (e.g., observational, secondary analysis, single/double blind, parallel, crossover, deception, etc.).

- **Clinical Research:** Indicate whether subjects will be randomized and whether subjects will receive any placebo.
- **Community-Based Participatory Research:** If you are conducting [community-based participatory research \(CBPR\)](#), describe strategies for involvement of community members in the design and implementation of the study, and dissemination of results from the study.
- **Qualitative research:** Indicate ranges where flexibility is needed, if a fixed interview transcript is not available, describe interview topics including the most sensitive potential questions.
- **Research Repositories:** If the purpose of this submission is to establish a Research Repository (bank, registry) and the material you plan to collect is already available from a commercial supplier, clinical lab, or established IRB approved research repository, provide scientific justification for establishing an additional repository collecting duplicate material. Describe the repository design and operating procedures. For relevant information to include, see the [UK Research Biospecimen Bank Guidance](#) or the [UK Research Registry Guidance](#).

This is a prospective, non-blinded, non-randomized study to assess the impact of CRRT on critical illness muscle wasting. As the study is observational and non-interventional in nature, there will be no placebo administered in the course of the study. Patients will be identified based on conversations with ICU and Nephrology consult teams (in addition to chart screening) to determine which patients are likely to receive RRT therapy due to AKI and critical illness. In the first aim, patients will undergo musculoskeletal ultrasound (MKUS) assessments within 24 hours of CRRT initiation, and again at 48 hours and 168 hours. In addition, blood will be drawn at these timepoints and stored for later analysis. In Aim 2, the trajectory of muscle mass recovery will be determined through visits at the time of hospital discharge (to be completed within the hospital), and then at 1 and 3 months thereafter, which will entail separate visits. At these sessions, patients with AKI-RRT and matched controls will undergo measurements of muscle mass, strength, and function at hospital discharge and at 1- and 3-months following discharge. Measurements will include MKUS to determine CSA and muscle echogenicity in the RF and TA muscles. We will evaluate muscle strength by measuring: 1) Medical Research Council sum score (MRC-ss), a measure of global peripheral muscle strength that is the current clinical standard for diagnosing ICU-AW34, 2) Maximal isometric knee extensor and dorsiflexion muscle strength measured as peak force production and rate of force development38, and 3) Maximal isometric grip strength 40. Muscle power will be measured by the repetitive 5x sit-to stand test a reliable and validate measure of lower-extremity power. Physical function and frailty will be measured using 1) the Short Performance Physical Battery (SPPB), 2) six-minute walk test (6MWT), and 3) Clinical Frailty Scale. SPPB is a performance-based composite test with a total of 12 points including components of balance, chair to stand test, and 4-meter habitual gait speed. The 6-MWT assesses the distance a subject can walk in six minutes providing a global marker of physical function and representation of cardiopulmonary endurance. We will summarize descriptive statistics at each timepoint including mean and standard deviation or median and interquartile range, as appropriate. Independent t-tests and Mann-Whitney U tests for non-parametric data will be used as appropriate to compare differences in the testing outcomes between cases and controls at each timepoint. Two-way repeated measures ANOVA will be performed to assess the within change in muscle metrics over time and between group comparisons to understand the trajectories of muscle recovery.

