- Muscle strength/function assessment is anticipated to take 30-60 minutes.

Long-term follow-up and how it occurs

- Patients will be seen at 1 and 3 months follow-ups in the outpatient setting. Visit times and dates will be arranged prior to discharge if possible, or via telephone after discharge.

Variables collected from the chart will include the following:

- Demographic data (Age, Gender, Race, BMI)
- SOFA or APACHE score at initiation
- Comorbidities (Charlson Score)
- Cause of AKI (Sepsis, post-surgical, etc.)
- Location of ICU (medical vs surgical)
- Laboratory data at baseline (BMP, CBC, lactate, albumin, INR)
- Daily laboratory data
- % Volume overload at initiation and daily
- CRRT variables (BFR, dose, therapy fluid flow rate, UF, filtration fraction).
- Reason for filter loss
- Time to death (censored for patient drop out or loss to follow up)
- In-hospital Mortality
- Time to renal recovery (censored for interfering events)
- Renal Recovery at hospital discharge

What Control subjects will be asked to do/what happens in the study (in sequential order):

- At hospital discharge, the patient will undergo a series of muscle strength and function tests including 1)Medical Research Council sum score (MRC-ss), a measure of global peripheral muscle strength that is the current clinical standard for diagnosing ICU-AW, 2) Maximal isometric knee extensor and dorsiflexion muscle strength measured as peak force production and rate of force development, and 3) Maximal isometric grip strength. Muscle power will be measured by the repetitive 5x sit-to stand test a reliable and validate measure of lower-extremity power. Physical function and frailty will be measured using 1) the Short Performance Physical Battery (SPPB), 2) six-minute walk test (6MWT), and 3) Clinical Frailty Scale. SPPB is a performance-based composite test with a total of 12 points including components of balance, chair to stand test, and 4-meter habitual gait speed.

The time period over which procedures will occur:

- Muscle strength/function and MKUS will be assessed at hospital discharge, and at 1 and 3 months thereafter.

The time commitment for the subject for individual visits/procedures

- The time commitment will be 10-20 minutes for ultrasound procedures as above, and muscle strength/function assessment is anticipated to take 30-60 minutes.

Long-term follow-up and how it occurs

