## Records, Privacy, and Confidentiality

Specify where the data and/or specimens will be stored and how the researcher will ensure the privacy and confidentiality of both. Specify who will have access to the data/specimens and why they need access.

Describe how data will be managed after the study is complete:

- If data/specimens will be maintained, specify whether identifiers will be removed from the maintained information/material.
- If identifiers will not be removed, provide justification for retaining them and describe how you will protect confidentiality.
- If the data/specimens will be destroyed, verify that this will not violate [retention policies](#) and will adhere to applicable facility requirements.

If this study will use de-identified data from another source, describe what measures will be taken to ensure that subject identifiers are not given to the investigator.

If applicable, describe procedures for sharing data/specimens with collaborators not affiliated with UK.

For additional considerations:

[Return of Research Results or Incidental Research Findings](#)

[HIPAA policies](#)

[FERPA policies](#)

[Procedures for Transfer agreements](#)

[Information regarding multi-site studies](#)

[NIH Genomic Data Sharing \(GDS\) Policy](#)

[Digital Data](#)

Research materials will include biologic samples, ultrasound imaging, paper/hard copy records, and electronic records. Biologic samples will be taken in the form of blood draws and effluent collection. These samples are necessary for the assessment of amino acid loss in patients with AKI-RRT. Ultrasound imaging is necessary for the assessment of muscle loss in patients in an ICU setting. Hard copy/electronic records are necessary for the screening and enrollment process.

Biologic samples - We will use a coding system rather than directly identifying information on the specimens. The code will be stored in REDCap. Samples will be stored in a secure lab space.

Paper/hard copy records - After signed consent is obtained, a copy will be made and given to the patient or LAR. The original consent documents will be given to the PI, and kept in a secure location that will be locked when not in use. Paper records, where applicable, will be stored at [name]. This room is locked at all times when unoccupied.

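### The study is declared non-blinded with no exception for reading ultrasound images, so muscle size may be measured with knowledge of group and visit

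*Protocol*

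**What the plan says.** Study Design opens its description with the words "This is a prospective, non-blinded, non-randomized study". No part of the conduct is exempted from this. The same section names the ultrasound measures: "Measurements will include MKUS to determine CSA and muscle echogenicity in the RF and TA muscles".

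These measures matter to the aims. Under Objectives, Hypothesis 1 reads: "Patients with AKI-RRT have faster decline in rectus femoris and tibialis anterior muscle size compared to controls". Its comparator is historic: "Determine the rate and degree muscle wasting in critically ill patients with AKI-RRT vs historic ICU controls without AKI during ICU stay". Aim 2 compares recovery of muscle mass, strength, power and function with matched controls. Study Design has both groups measured at hospital discharge and at 1 and 3 months, and the control part of Research Procedures confirms it: "Muscle strength/function and MKUS will be assessed at hospital discharge, and at 1 and 3 months thereafter".

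On materials, Records, Privacy, and Confidentiality states: "Research materials will include biologic samples, ultrasound imaging, paper/hard copy records, and electronic records". For the biologic samples, it adds: "We will use a coding system rather than directly identifying information on the specimens". It describes no coding, archive or reading procedure for the images.

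**The concern.** Observers cannot be masked during bedside scanning or a walking test. Tracing a muscle border or grading echogenicity is different, because it can be done on a saved image that carries no group or visit label. The tracing involves judgement, and the protocol states in advance what is expected of cases: faster loss in the ICU and slower recovery afterwards. A reader who knows that an image is a case's later scan can move the border a little without intending to.

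The Background section cites excellent inter-rater reliability for ultrasound. That is agreement between readers, and readers who share an expectation can agree and still be biased.

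At stake are the between-group comparison in Hypothesis 1 and the muscle-mass comparison in Aim 2. Aim 1 is the more exposed. Its controls are historic, so their measurements presumably exist already, and an expectation effect in the new reads could fall on the cases alone.

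**Working it through.** The protocol gives no figure for reader error, effect size, standard deviation, alpha or power, so there is no stated number to reproduce. The check is mainly of the text.

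**1. Is masked reading provided anywhere?**
- Study Design: non-blinded, without exception.
- Research Procedures: timing and duration of the scans, but no reader and no reading procedure.
- Records, Privacy, and Confidentiality: ultrasound imaging is listed as research material; coding is described for specimens only.
- No section provides masked, independent or centralised reading.

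**2. Which aims depend on the reading?**
- Aim 1: wholly, since Hypothesis 1 concerns muscle size.
- Aim 2: in part, since strength, power and function are measured as well.
- Aim 3: ultrasound supplies the muscle measure, but it is related to amino acid trends, and Study Design says blood is stored for later analysis. A reader tracing near the time of the scan would not know those trends.

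**3. Is masked reading feasible?**
- Aim 2: cases and controls are scanned within this study at the same three visits, so both group and visit can be hidden.
- Aim 1: visit can be hidden for cases. Group can be hidden only if the historic control images still exist and are re-read with the new ones.
- Care: Potential Risks & Benefits says findings do not go to the primary team and do not inform care, so delayed reading has no clinical consequence.
- Workload: Project Information sets a maximum of 60 subjects.

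**4. How much could it matter?** The size of any reader shift is not in the documents, so this step is illustrative. Assume a two-sided alpha of 0.05, no true difference, and a systematic shift of b standard deviations between groups. With SE = √(1/n₁ + 1/n₂), and Φ the standard normal distribution function, the false-positive rate of a z-test is

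Φ(b/SE − 1.96) + Φ(−b/SE − 1.96).

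For 30 vs 30 and b = 0.2: SE = √(2/30) = 0.258 and b/SE = 0.775. The rate is Φ(−1.185) + Φ(−2.735) = 0.118 + 0.003 = 0.121.

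| Assumed split | b = 0 | b = 0.1 | b = 0.2 | b = 0.3 | b = 0.5 |
|---|---|---|---|---|---|
| 30 vs 30 | 0.05 | 0.067 | 0.121 | 0.213 | 0.491 |
| 20 vs 40 | 0.05 | 0.065 | 0.113 | 0.195 | 0.447 |
| 15 vs 15 | 0.05 | 0.059 | 0.085 | 0.130 | 0.278 |

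The protocol does not split its 60 subjects between cases and controls, so the group sizes are assumptions too. The b = 0 column is what masked reading aims for, as far as the reader's contribution goes.

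**The case against.** The strongest reply is that the word non-blinded answers a form prompt about design type, randomisation and placebo, and that the next sentence explains the absence of placebo by the observational design. On that reading it describes allocation and says nothing about image reading. The form accepts summaries, and its attachment list names a separate protocol file that is not at hand and could hold a reading procedure. This stands in part. A reader might infer that the protocol prescribes unblinded tracing. It does not; it leaves tracing undescribed under a blanket statement that the study is not blinded.

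Three other replies are sound:
- Listing ultrasound imaging as research material does not establish that still images are archived and traced offline, and the specimen coding does not cover images. The amendment has to state both.
- Only de-identified data move between sites, so pooled reading masked to site would require image sharing that the protocol does not provide for.
- If the person who scanned the patient also traces the image, removing labels may not mask that person.

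A reader might also infer that the bias favours all three hypotheses, or that it could never be repaired. Neither is supported. Amino acid levels would not be known to someone reading near the time of the scan, so the directional argument does not reach Aim 3. If images are kept, a masked re-read stays possible later.

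Finally, one might try to express the bias as a share of the expected muscle loss. The documents give no reader shift, the Background loss figures cover ten days rather than seven, and Hypothesis 1 tests a difference between groups rather than absolute loss. No such percentage can be given.

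**Conclusion.** The point holds as a modest, avoidable weakness of design. The protocol calls the study non-blinded without exception and provides no masking for a reader-dependent measure, so the Hypothesis 1 outcome and the muscle-mass part of Aim 2 may be read with knowledge of group and visit. The observational design accounts for the absence of placebo and treatment blinding, but it gives no reason against masking the image reader.

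The size of the bias is unknown. The illustrative rates show only that, with groups this small, shifts of a few tenths of a standard deviation would matter; they do not show that such shifts will occur. No outcome is labelled primary, so the importance given to muscle size rests on its place in Hypothesis 1. The conclusion assumes that images can be saved and measured away from the bedside, and that no document outside this one already provides masked reading.

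**What to change.** Add a short statement to Study Design or Research Procedures:
- Ultrasound images are saved under the study code, extending the coding already used for specimens.
- Current trained staff at each site trace cross-sectional area and grade echogenicity in random-order batches without group or visit labels, preferably not the person who scanned that patient. Masking to site is not required.
- For Aim 1, historic control images are re-traced in the same batches if they are stored. If they are not, case reads are masked to visit only, and the report says that the group comparison is not reader-masked.

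The cost is some file handling and a delay before measurements are available. Sample size, visits and patient procedures do not change. Bias from bedside image acquisition and from the functional tests remains and should be acknowledged.
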